# 8.3.3.2 RELATIONSHIP TO STUDY INTERVENTION

The Site PI or delegated study physician at each site must assess the relationship between investigational product (study drug) and each AE/SAE. The study physician will use clinical judgment to determine the relationship. Alternative causes, such as natural history of the underlying diseases, concomitant therapy, other risk factors, and the temporal relationship of the event to the investigational product will be considered.

The degree of certainty about causality will be graded using the categories below.

Version 4.0

ALIVE Study 21st January 2022

Definite: The adverse event has a strong temporal relationship to study drug and/or recurs on re-

challenge, and cannot be explained by an alternative aetiology.

Probably: The adverse event has a strong temporal relationship to study drug or recurs on re-challenge,

and an alternative aetiology is unlikely or significantly less likely.

Possibly: The adverse event has a strong temporal relationship to the study drug, and an alternative

aetiology is equally or less likely compared to the potential relationship to study drug. The

alternate aetiology should be provided by the investigator.

Unlikely: The adverse event has little or no temporal relationship to the study drug and/or a more

likely alternative aetiology exists. The alternate aetiology should be provided by the

investigator.

Unrelated: The adverse event is due to underlying or concurrent illness or effect of another drug and is

not related to the study drug. The alternate aetiology should be provided by the investigator.

The categories "unrelated" and "unlikely" will be mapped to "unrelated", the categories "possible", "probable" and "definite" will be mapped to "related".

#### 8.3.3.3 SUSPECTED UNEXPECTED SERIOUS ADVERSE REACTIONS (SUSARS)

The Site PI or delegated study physician will be responsible for determining whether an AE is expected or unexpected. An AE will be considered unexpected if the nature, severity, or frequency of the event is not consistent with the risk information previously described for the study intervention. Such adverse events are called SUSARS. That is any SAE where a causal relationship with the study drug is at least reasonably possible but is not listed in the reference safety information section of the investigators brochure (IB).

#### 8.3.4 TIME PERIOD AND FREQUENCY FOR EVENT ASSESSMENT AND FOLLOW-UP

The occurrence of an AE or SAE may come to the attention of study personnel during study visits and interviews of a study participant during a study visit, or upon review by the study monitor.

All AEs including local and systemic reactions not meeting the criteria for SAEs will be captured in the CRF. Information to be collected includes event description, time of onset, the study physician's assessment of severity, relationship to study drug, and time of resolution/stabilization of the event. All AEs that occur

stercoralis) in Paediatric and Young Adult Population

Version 4.0

ALIVE Study 21st January 2022

during the study duration must be documented appropriately regardless of the relationship. All AEs will

be monitored to adequate resolution.

Any medical condition that is present at the time that the participant is screened will be considered as

baseline and not reported as an AE. However, if the study participant's condition deteriorates at any time

during the study, it will be recorded as an AE.

Changes in the severity of an AE will be documented on the source documents to allow an assessment of

the duration of the event at each level of severity to be performed. AEs characterized as intermittent

require documentation of onset and duration of each episode.

8.3.5 ADVERSE EVENT AND SERIOUS ADVERSE EVENT REPORTING

All AEs that meet the definition of SAE will be reported to the Sponsor by the Site PI or delegated study

physician or an assigned representative within 24 hours of the site becoming aware of it, using a study

SAE form located in the Investigators Folder (IF), which should be completed, scanned and sent via email

to the Sponsor.

8.3.6 REGULATORY REPORTING OF SAES

SAE reporting by each site, will comply with local regulations for SAE reporting to the sites EC/IRB and

regulatory authorities.

58

Version 4.0

**ALIVE Study** 

21st January 2022

All unexpected SAEs must be reported to the ethics committee within 15 days (7 days in case of death) from knowing of the SAE. In addition to the expedite SAE reporting in 24h, monthly aggregate and annual reports will be written by the Site PI or delegated study physician at each site.

A copy of the final study report will be provided to the regulatory authorities for each country and the DSMB.

In addition, ISGlobal will report all SAEs to the DSMB as well as the CEIm (EC for ISGlobal). ISGlobal will also report any SUSAR to EudraVigilance (EU) and will notify all the study site PIs as soon as possible.

#### 8.3.7 PREGNANCY

Participants who are ≥12 years old (or post menarche) must have a negative urine pregnancy test to be enrolled into the study. No further pregnancy test will be performed. The duration of the study is 21 (+/-7days). Female participants ≥12 years old will be advised against pregnancy.

In the unlikely event of pregnancy during the trial, pregnancy must be reported to the Sponsor Pharmacovigilance team ([contact]) by the Site PI or delegated study physician within 24 hours of the site becoming aware of it, using a study Pregnancy notification form located in the Investigator's Folder. The investigator must follow up on pregnancies discovered after IP administration until delivery and document the outcome on a new *Pregnancy notification form*, clearly marked as follow-up report. The event fulfils the criterion for an SAE in case of a congenital anomaly (birth defect), foetus death or spontaneous abortion, or adverse events in the neonate that are classified as serious.

Version 4.0 21st January 2022

ALIVE Study

#### 9 STATISTICAL CONSIDERATIONS

#### 9.1 STATISTICAL HYPOTHESES

The main hypothesis is that FDC (either at single or 3-day regimens) will be more effective against STH than the current strategy (single dose ALB alone).

# Specific hypotheses:

- Primary Efficacy Endpoint: Higher estimated CR for *T. trichiura* 21 days after treatment using microscopy in participants allocated to arms 2 and 3 than to arm 1.
- Secondary Efficacy Endpoint(s):
  - Higher estimated CR for hookworm and S. stercoralis 21 days after treatment using microscopy in participants allocated to arms 2 and 3 than to arm 1.
  - Higher estimated ERR for hookworm, *T. trichiura* and *S. stercoralis* 21 days after treatment using microscopy in participants allocated to arms 2 and 3 than to arm 1
  - Higher estimated CR for hookworm, T. trichiura and S. stercoralis 21 days after treatment using PCR in participants allocated to arms 2 and 3 than to arm 1.

#### 9.2 SAMPLE SIZE

Sample size was calculated based on available data from peer-review publications complemented with reasonable estimates of efficacy for those experimental groups that have not been previously tested. Given the public health relevance of generating data for each species of STH of interest to this trial, sample size calculations are made to provide adequate power for each of these species, including that in the primary endpoint (*T. trichiura*) and those in the secondary endpoints (hookworms and *S. stercoralis*). For these calculations, the efficacy of the control arm (Albendazole 400mg in a single dose), was obtained for *T. trichiura* and hookworms from a systematic review and meta-analysis where temporary trends in efficacy (with the corresponding confidence intervals) were incorporated (Table 3)(4). For the efficacy of the control arm against *S. stercoralis*, an alternative source was used since the systematic review by *Moser* (54) *et al* did not include this species; for that reason, a clinical trial that included an arm of Albendazole 400mg for 3 consecutive days was used, assuming a "best case scenario" for the efficacy of the control group; this estimated efficacy is also in the range of a systematic review assessing the efficacy of Albendazole at various (but not single) doses (54). For the FDC at single dose, the calculations were based

Version 4.0

ALIVE Study 21st January 2022

on the estimated efficacies (and their corresponding confidence intervals) in a systematic review that calculated the Relative Risks of cure of diverse drug regimens against Albendazole 400mg single dose (Table 3)(30,55). For. *S. stercoralis*, the estimated efficacy of FDC was calculated based on a recent clinical trial using Ivermectin single and multiple-dose regimens(56). Finally, for the FDC in 3-dose regimens, considering its use in public health, deployment logistics in MDA campaigns and expected impact of the FDC, we estimated that an improvement of at least 15 percentage points would be the minimum

improvement in efficacy to be demonstrated in order to make the FDCx3 regimen worth considering.

Sample size was calculated estimating the efficacy of the different experimental drug or combinations for each of the STH of interest (57,58), and gathering the individual samples sizes for the study. The sample size was calculated for pairwise comparisons of the expected Cure Rates for three study groups with an overall significance level of 5% adjusted for multiple tests by Bonferroni's correction, 80% power and inflated for 10% lost-to-follow-up.

The estimated total number of participants for the adaptive design is 1223 (*T. trichiura* 625, *S. stercoralis* 286 and hookworm 312). This sample size is powered to be able to measure efficacy for all three species in the phase III component. The sample size for the phase II component is 20% of the total participants for *T. trichiura* (126 participants). The remaining 80% of the *T. trichiura* participants will be randomised in the phase III component. Table 2 details the stratification of the participants per species with a 10% lost-to-follow-up.

The total number of participants to be included in this clinical trial is 1223 (126 in phase II and 1097 in phase III). Following randomisation, 251 participants will be allocated to the ALB treatment arm, 427 will be allocated to the FDC treatment arm and 419 in the FDCx3 treatment arm. Table 2 details the stratification of the participants per species with a 10% lost-to-follow-up.

The 10% lost-to-follow-up inflated sample sizes of the ALB-group for *T. trichiura*, *S. stercoralis* and hookworm are 129, 47 and 101 respectively, and the corresponding sample sizes of the individual experimental treatment groups are 248, 120, and 101 for FDC-group and 248, 119 and 110 for FDCx3-group. The corresponding powers of each of the tests are 91%, 100% and 80% to compare the CRs of *T. trichiura* in ALB *vs* FDC, ALB *vs* FDCx3 and FDC *vs* FDCx3 respectively; 95%, 100% and 80% to compare the

Version 4.0 21st January 2022

ALIVE Study

CRs of *S. stercoralis* in the above-mentioned comparisons and 82%, and 80% to compare the CRs of hookworm respectively for ALB vs FDCx3 and FDC vs FDCx3 comparisons. We do not compare CRs of hookworm in ALB and FDC as they are known to be the same. These powers were computed assuming that the expected CRs for *T. trichiura* are 23.7%, 43.7% and 59% in the ALB, FDC and FDCx3 groups respectively; 45%, 79% and 94% for *S. stercoralis* and 79.5%, 79.5% and 95% for hookworm. **Table 1** and **Table 2** show the sample size calculation according to the expected Cure Rate for each drug and helminth of interest, and the resulting sample size inflated by 10% due to the estimated lost-to-follow-up. Assumptions used for the sample size calculations (e.g. expected CRs, lost-to-follow-up, etc) should be checked during the interim analysis.

Table 1. Sample size and power calculation according to the expected efficacy (Cure Rate) of the different treatment arms

Comparison	Target Power	Actual Power	Sample Size	Expected Cure Rate	Overall Alpha	Bonferroni adjusted Alpha
Trichuris trichiura						
ALB			116	23.7%		
vs IVM-ALB	80%	91%	223	43.7%	0.05	0.0167
vs (IVM-ALB)x3	80%	100%	223	59%	0.05	0.0167
IVM-ALB vs (IVM-ALB)x3	80%	80%			0.05	0.0167
Strongyloides stercoralis						
ALB			42	45%		
vs IVM-ALB	80%	95%	108	79%	0.05	0.0167
vs (IVM-ALB)x3	80%	100%	107	94%	0.05	0.0167
IVM-ALB vs (IVM-ALB)x3	80%	80%			0.05	0.0167
Hookworm						
ALB			91	79.5%		
vs IVM-ALB	80%		91	79.5%	0.05	0.0167
vs (IVM-ALB)x3	80%	82%	99	95%	0.05	0.0167
IVM-ALB vs (IVM-ALB)x3	80%	80%			0.05	0.0167

Version 4.0 21st January 2022

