The analytes of interest were H2B1a (97.2% of the total IVM), H2B1b (1.9% of the total IVM) for test product, and H2B1a: 99.0% - H2B1b: 1.5% for reference product Stromectol, ALB and ALB sulfoxide.  $C_{max}$  and  $AUC_{0-72}$  of  $H_2B_{1a}$  and  $H_2B_{1b}$  were the primary pharmacokinetic parameters for the comparison of bioequivalence for IVM.  $C_{max}$  and  $AUC_{0-t}$  of ALB and ALB sulfoxide were the primary pharmacokinetic parameters for the comparison of bioequivalence for albendazole.

The test /reference (T/R) geometric mean ration and the corresponding 90% Confidence Intervals for the primary PK metrics of interest are provided in Table 1.

Table 1. T/R GMR and the corresponding 90% Confidence Intervals for  $C_{max}$  and AUC for  $H_2B_{1a}$ ,  $H_2B_{1b}$ , Albendazole and Albendazole sulfoxide.

	H 2 B 1a	H 2 B 1b	Albendazole	Albendazole
				sulfoxide
C max	115.48 (110.68 –	164.86 (155.87 –	61.11 (53.10 –	76.56 (70.99 –
	120.49%)	174.37%)	70.34)	82.56)
AUC 0-72	114.94 (110.46 –	169.80 (158.54 –	-	-
	119.60%)	181.85%)		
AUC 0-t	-	-	68.40 (61.13 -	81.13 (75.93 –
			76.54)	86.69)

In summary, the Phase I study results revealed that for the moiety H2B1a the results regarding rate and extent of absorption indicate bioequivalence between Test and Reference, whereas for the moieties H2B1b, ALB and ALB sulfoxide bioequivalence could not be inferred. Importantly, concerning the secondary objective of safety and tolerability, no serious adverse event occurred during the bioequivalence study with only mild (n=51) and moderate (n=11) events reported, supporting the safety profile of the FDC.

Version 4.0

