**ALIVE Study** 

21st January 2022

Since the efficacy and safety of the new FDC product will be tested in the adaptive phase II/III trial, the obtained test/reference ratios are considered primarily "for description purposes only" and any incompliance with the 80-125% range is considered exceptionally still acceptable for the fixed drug combination (FDC) tablets as long as no major safety issues arose with the FDC in the Phase I study.

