## 9.5 STATISTICAL ANALYSES

#### 9.5.1 GENERAL APPROACH

A Statistical Analysis Plan (SAP) for the trial will be developed. Two interim efficacy analyses are planned:
1) after the end of the phase II component for decision making to move to the phase III component; 2) after 50% of the study participants are enrolled. Regular evaluation of the safety data every 3 months will be performed by the DSMB. The study is designed as a superiority trial, so all tests will be two-sided and all statistical significance will be declared at the 0.05 level. Analysis will be done using R.

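### The hookworm cure rates of single-dose FDC and ALB are called known to be equal, hypothesised to differ, and given no contrast of their own, although Phase I found lower albendazole exposure from the FDC

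*Protocol*

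**What the plan says.** **Sizing.** Protocol 9.2 and SAP 3.5 take hookworm cure rates of "79.5%, 79.5% and 95% for hookworm" (ALB, FDC, FDCx3) and then say: "We do not compare CRs of hookworm in ALB and FDC as they are known to be the same". Protocol Table 1 (SAP Table 3) gives the ALB versus single-dose FDC row for hookworm an 80% target and leaves the actual power blank.

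**Hypotheses.** Protocol 9.1, repeated in SAP 5.3.1, lists as a secondary hypothesis "Higher estimated CR for hookworm and S. stercoralis 21 days after treatment using microscopy in participants allocated to arms 2 and 3" than in arm 1.

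**Phase I.** Protocol 2.2 (comparative bioavailability study) gives these FDC/reference ratios with 90% confidence intervals:

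| | Cmax | AUC0-t |
|---|---|---|
| Albendazole | 61.11% (53.10 to 70.34) | 68.40% (61.13 to 76.54) |
| Albendazole sulfoxide | 76.56% (70.99 to 82.56) | 81.13% (75.93 to 86.69) |

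It concludes for H2B1a that the products are bioequivalent, "whereas for the moieties H2B1b, ALB and ALB sulfoxide bioequivalence could not be inferred". The same section treats values outside 80-125% as acceptable, provided Phase I raised no major safety issue, and opens its reason with "Since the efficacy and safety of the new FDC product will be tested in the adaptive phase II/III trial".

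**Analysis.** SAP 5.4.1 analyses hookworm cure rate in the same way as the primary endpoint. SAP 5.4 defines that as a CMH test across the three treatment groups, controlling for site if appropriate, in the ITT population. SAP 4.1 and 5.1.5 count missing efficacy data as failure. No ALB versus FDC contrast, interval or margin is given for hookworm.

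**The concern.** One contrast has three incompatible descriptions: the rates are equal and not compared, arm 2 is higher, and all three arms are tested together. An analyst cannot follow all of them.

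The word *known* is the weak point. Both 90% intervals for albendazole itself lie wholly below 80%. Protocol 4.2 says ivermectin alone has low efficacy against hookworm, so the ivermectin component cannot be relied on to make up a shortfall. Protocol 2.2 also cites hookworm cure rising from 45% to 79% with three days of ALB, so response varies with the ALB regimen. Having accepted the Phase I ratios on the ground that efficacy will be tested here, the protocol declines the hookworm contrast to which those ratios matter most.

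The FDC is intended for all STH (Protocol 2.2), so whether a single tablet keeps ALB's hookworm effect matters to anyone deciding on its use. A three-group result driven by FDCx3, set beside a hypothesis naming arms 2 and 3 together, could be misread as covering arm 2.

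**Working it through.** **1. Inputs.** Hookworm cure rates are 79.5%, 79.5% and 95%. Evaluable numbers are 91, 91 and 99 (Protocol Table 1), inflated to 101, 101 and 110 (Protocol Table 2). The sizing rule is "overall significance level of 5% adjusted for multiple tests by Bonferroni's correction, 80% power and inflated for 10% lost-to-follow-up", which gives 0.0167 per comparison, and tests are two-sided (Protocol 9.5.1).

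**2. The plan's own figure.** For 79.5% against 95% with n = 91 and 99:
- Pooled rate = (91 × 0.795 + 99 × 0.95)/190 = 0.876.
- Null SE = √[0.876 × 0.124 × (1/91 + 1/99)] ≈ 0.0479. Alternative SE = √[0.795 × 0.205/91 + 0.95 × 0.05/99] ≈ 0.0477.
- Power = Φ[(0.155 − 2.394 × 0.0479)/0.0477] ≈ 80.1%.

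The plan states 80% and 82% for its two hookworm comparisons, so the sizing reproduces to within 2 points.

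**3. What the three-group test shows.** An unstratified 2-df chi-square at 0.05 was simulated with n = 91/91/99 (20,000 runs). It stands in for the CMH test without site strata. The 10-point loss is an assumption; the documents give none.

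| True cure rates ALB / FDC / FDCx3 | Significant |
|---|---|
| 79.5% / 79.5% / 95% | about 94% |
| 79.5% / 69.5% / 95% | about 99.7% |

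The test is nearly always significant in both cases because FDCx3 drives it, and slightly more often when single-dose FDC is worse.

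**4. Power of a direct ALB versus FDC test.** With 91 per arm and a true loss of 10 points at two-sided 0.05:
- Null SE = √(2 × 0.745 × 0.255/91) = 0.0646. Alternative SE = √[(0.795 × 0.205 + 0.695 × 0.305)/91] = 0.0642.
- Power = Φ[(0.10 − 1.96 × 0.0646)/0.0642] ≈ 34%.

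| Assumed loss | Power at 0.05 | Power at 0.0167 |
|---|---|---|
| 5 points | 12% | 5.5% |
| 10 points | 34% | 20% |
| 15 points | 62% | 44% |
| 20 points | 84% | 71% |

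**5. Precision of FDC minus ALB if the true rates are equal.** Half-width = 1.96 × √[p(1 − p)(1/n₁ + 1/n₂)].
- Evaluable, 91/91, p = 0.795: 1.96 × √(2 × 0.795 × 0.205/91) = 11.7 points.
- ITT with 10% missing counted as failure, p = 0.9 × 0.795 = 0.7155, 101/101: 1.96 × √(2 × 0.7155 × 0.2845/101) = 12.4 points.
- The same under the 0.2/0.4/0.4 allocation in SAP 3.3, where 312 × 0.2 ≈ 62 and 312 × 0.4 ≈ 125: 1.96 × √[0.7155 × 0.2845 × (1/62 + 1/125)] = 13.7 points.

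The last two assume equal missingness in both arms. The documents disagree on allocation: Protocol 4.1 says 1:1:1, SAP 3.3 says 0.2/0.4/0.4, and Table 2 has 101/101/110 for hookworm.

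**6. What such an interval can exclude.** At 91/91 with truly equal rates, SE = 0.0598. The interval excludes a 10-point loss with probability Φ(0.10/0.0598 − 1.96) ≈ 39%, and a 12-point loss with probability of about 52%.

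**The case against.** **The comparison is not dropped from the trial.** The sentence sits among power statements and explains an empty table cell. Hookworm cure rate is analysed in all three arms, egg reduction is compared by ANCOVA, and PCR cure rates follow (SAP 5.4.1). Arm-level rates will exist. This stands: what is missing is a powered or pre-specified contrast, not the data.

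**A reader might infer that a loss of hookworm efficacy could pass as success.** The documents do not support that. The primary endpoint is *T. trichiura* alone, hookworm cure is secondary, and no hookworm success rule exists. Tests are two-sided, and a lower arm 2 estimate would not meet a hypothesis of a higher rate. The risk is one of misreading.

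**A reader might also infer that Phase I shows a loss.** It does not. It measured plasma exposure in healthy adults, used only the 18 mg strength (Phase III gives 9 mg below 45 kg), and took as reference a named albendazole brand that the documents do not identify with the trial's chewable comparator. No section links plasma exposure to hookworm cure: the 45% to 79% rise concerns repeated dosing, and the ivermectin statement concerns monotherapy.

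**The lack of pairwise contrasts is general.** SAP 5.4 names none for any species, so deleting the quoted sentence would not cure it. That is true, but hookworm is the species for which the plan also declares two arms equal.

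**Conclusion.** The concern holds as a contradiction combined with an unpowered comparison that has no pre-specified contrast. Equality of the two hookworm rates is a sizing assumption worded as a known fact, and it conflicts with the stated arm 2 hypothesis. The Phase I ratios make a loss plausible without showing one.

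The planned three-group test cannot speak for arm 2: it is significant in about 94% of trials with no difference between FDC and ALB, and in over 99% with an assumed 10-point loss. A direct comparison at 91/91 has about 34% power for that loss. The 95% half-width is 11.7 points in evaluable participants and 12.4 to 13.7 points under the planned ITT rule with 10% missing.

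These figures rest on the plan's own cure rates, normal approximations and an unstratified stand-in for CMH. The sizing calculation itself is sound. This should be fixed; it is not more serious than that, because hookworm is secondary and carries no success rule.

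**What to change.** 1. **Protocol 9.2 and SAP 3.5:** replace the claim of known equality with wording such as *assumed equal for sizing only; this comparison is not powered*.
2. **SAP 5.4.1:** pre-specify the hookworm cure-rate difference, FDC minus ALB, with a two-sided 95% confidence interval, labelled as estimation. State that a significant three-group test alone supports no claim for arm 2.
3. **Protocol 9.1 and SAP 5.3.1:** reconcile the arm 2 hookworm hypothesis with the equality assumption, either by limiting superiority to arm 3 or by marking arm 2 as estimation only.
4. **SAP 3.5 or 5.4.1:** state the expected precision under ITT with 10% missing counted as failure: about 12.4 points at 101/101, or 13.7 at about 62/125, against 11.7 at 91/91 evaluable. Add that power for a true 10-point loss at 91/91 is about 34%. Settle the allocation ratio first, since it changes these figures.

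**Cost.** No new participants or data are needed. The protocol wording is an amendment requiring ethics approval (Protocol 10.1). The added interval may show a loss, or be too wide to exclude one. Showing non-inferiority instead would need a justified margin and usually more participants: at equal rates, one-sided 0.025 and 80% power, a 10-point margin needs 256 evaluable per arm and a 15-point margin 114.
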